## 1. Introduction and Background

In the Children’s multimedia study, we propose to investigate the effects of media multi-tasking on child obesity. The modern obesogenic environment is replete with cues to eat. Environmental food cues stimulate brain reward regions and lead to excess consumption independent of hunger levels (1). This cued eating is partially mediated by the amount of attention given to food cues. For example, children who spend more time looking at food cues consume more calories than children who do not (2). We propose that the prevalent practice of media multi-tasking—simultaneously attending to multiple electronic media sources—increases attention to peripheral food cues and subsequent cued eating and thereby plays an important role in the development of obesity. Neural networks are responsible for controlling attention to peripheral cues. The dorsal and ventral orienting networks control the shifting and focusing of attention, and the frontoparietal network controls the filtering of peripheral cues in the environment (3-5). Media multi-tasking is known to increase orienting and decrease the filtering abilities associated with these networks (6-8). By this mechanism, we propose that media multi-tasking increases obesity risk by increasing attention to peripheral food cues. Current efforts to address obesity ignore this prevalent risk behavior. Fortunately, it is possible to improve the functioning of the attentional networks through attention modification training (9); thus this research examines the hypothesis that attention modification training can decrease the amount of attention children give to food cues.

## Theoretical Model

We propose that the persistence of childhood obesity (Figure 1) is caused, in part, by the rise in media multi-tasking that alters attention to peripheral cues, rendering some children more susceptible to cued eating. We expect that high levels of media multi-tasking weakens the attentional network responsible for filtering out distracting environmental cues (frontoparietal network) and strengthens the attentional networks responsible for shifting and focusing attention to peripheral cues (ventral and dorsal orienting attentional networks) (3-5). We theorize that by altering these attentional networks, media multi-tasking renders children particularly susceptible to food cues, thereby leading to cued eating. The functioning of attentional networks can be modified through attentional training that improves sustain attention, which we expect can provide a protective effect against overeating by decreasing attention to food cues.

## **Media multi-tasking is an increasingly prevalent exposure that may have important public health consequences.**

Children's ownership of diverse media devices is increasing. For example, ownership of a cell phone went from fewer than 40% of children in 2004 to 66% by 2009, and the use of iPods/MP3 players increased from 18% to 76% during that period (14). With this rise in device ownership is a concurrent rise in media multi-tasking; from 1999 to 2009 children nearly doubled their time spent media multi-tasking, from 16% of the time to 29% of the time that they were using media (14). Critically, this trend shows no signs of slowing. From 2011 to 2013, children's access to mobile devices increased from 52% to 75%(15), and although there is a scarcity on the reporting of media multi-tasking in children, our own preliminary data suggests that 60% of children are engaging in the practice (C.1.1). Thus far, the effects of multi-tasking on cued eating have not been examined. Given that one in three children in the United States is overweight or obese (16) and that excess weight in childhood increases the lifelong risk of many health problems (17-21), understanding why children gain excess weight and how to prevent it is essential to the NIH's mission of improving our nation's health.

## **Food cues activate brain reward systems that prompt cravings and eating.**

Though complex neural regulatory systems monitor the body's energy stores and prompt feeding behaviors to match energy requirements (22), non-homeostatic (hedonic) mechanisms also drive consumption of highly palatable foods (23,24). The dopaminergic mesolimbic pathway is central to hedonic eating because it detects rewarding food stimuli and prompts cravings and eating (25). In addition to the sight and smell of actual food, neuroimaging studies from our group (1,25) and others (26,27) demonstrate that images of food also stimulate this pathway and that food-cue-related activity in this pathway is related to subsequent snack food consumption (28) and weight gain (25). Limiting non-homeostatic cued eating is essential for healthy weight maintenance, because even modest caloric excesses can accumulate into substantial weight gain over time (29,30).

## **Media multi-tasking may alter neural attentional networks and thereby increase attention to food cues and prompt greater consumption.**

Attention to peripheral food cues is controlled by a series of attentional networks. The frontoparietal attentional network is responsible for filtering distracting environmental cues, and the ventral and dorsal orienting attentional networks are responsible for shifting and focusing attention to peripheral cues (3-5). Research has shown that these networks undergo a critical developmental period during childhood in which changes that occur during this period often track into adulthood (11). Frequent media multi-tasking has been associated with increased attention to peripheral cues. This result was documented by Nass and colleagues who studied how an individual's self-report of light or heavy usual media multi-tasking related to their performance on well-established behavioral paradigms of attention (8). Neuroimaging studies have shown that media multi-tasking is associated with activity in brain areas of the frontoparietal attentional network (6), and our own pilot data has shown that high media multi-taskers have greater cue reactivity to extraneous food cues in known brain reward areas (C.1.2). Consistent with these findings, high media multi-taskers are known to have a greater spread of attention to peripheral cues (7). These studies are based on a well-established attentional network theory of attention (3-5) and provide converging behavioral and neuroimaging evidence that high media multi-taskers are particularly susceptible to the influence of peripheral cues. The cross-sectional nature of these past studies limits inference about the direction of causality between media multi-tasking and attention to peripheral cues. We will address this limitation in the literature through our controlled experimental design. In addition, no studies have considered the effects of media multi-tasking on attention to food cues and consumption. The effect of media multi-tasking on attention to environmental food cues, specifically, is warranted because some evidence suggests that food cues require different attentional demands than less salient cues (31-33). There is a potentially large significance in understanding how media multi-tasking affects attention to food cues given that attention to food cues has been robustly related to consumption in both adults and children in a number of studies that have used a variety of attention paradigms (2,34,35).

## **Attentional training reduces attention to peripheral environmental cues.**

It is possible to decrease the amount of attention given to peripheral food cues through attention modification training (36-38). Research in adults (36) and children (9) support our contention that one-session attention modification training can decrease immediate consumption. In addition, a study of a large sample of undergraduates showed that activation of executive control using the Stroop Task reduced the amount of attention given to food cues in a subsequent dot-probe paradigm, suggesting that acute manipulations of attention can have immediate effects on the amount of attention given to food cues (39). This is consistent with the robust research in the anxiety domain that has shown one-time attention modification training can reduce the amount of attention given to threatening cues (40). To date, however, there have been no studies that have looked at the effect of attention modification training that improves sustained attention (AMT-S) on the amount of attention given to food cues. AMT-S may be particularly effective at reducing attention to peripheral food cues in children, because it is based on a translational neuroscience approach in which the therapeutic action directly targets the brain’s attentional networks, rather than specific types of cues. For example, research with neglect patients showed that AMT-S training produced increased activation in the superior parietal cortex and right and left frontal areas and anterior cingulate cortex. These brain regions have been associated with all three attentional networks (41,42). This generalized attention training may be the most effective given the heterogeneity of food cues in our current obesogenic environment. In addition, AMT-S interventions are uniquely promising because the mechanisms associated with sustained attention are the opposite of the automatic, poorly filtered attention thought to underlie the negative effects of media multi-tasking (43). For example, sustained attention is the ability to focus and self-sustain mindful, conscious processing of task-relevant stimuli that would otherwise lead to habituation and subsequent distraction to extraneous stimuli (44). Consistent with this suggestion, a short-term intervention that has been shown to improve sustained attention in undergraduates (45) has also been shown to reduce the maladaptive attentional processing associated with media multi-tasking. The study conducted with a large sample of young adults showed that AMT-S improved performance on a battery of attention tasks - including filtering and distractibility - in both high- and low-usual media multi-taskers, but this effect was greater for high media multi-taskers (43).

## 2. Objectives and Hypotheses

[figure not shown]
Our long-term goal is to understand the determinants of children’s individual susceptibility to environmental food cues and cued eating to develop interventions that reduce childhood obesity. Our overall objective is to determine how media multi-tasking affects attention to peripheral food cues and overeating, and whether it is possible to intervene on this proposed pathway. We have two central hypotheses. The first is that engaging in media multi-tasking increases attention to peripheral cues and thereby makes children more susceptible to environmental food cues (e.g., food advertising, sight or smell of food) that leads to cued eating in the absence of hunger. The second is that attentional training that improves sustained attention protects children against attention to peripheral food cues and therefore makes them less susceptible to cued eating.

## 3. Study Design

**Describe all study procedures, materials, and methods of data collection:**

We will achieve our aims by having 13-17-year-olds visit the laboratory on three occasions to complete each of three tasks: a media multi-tasking paradigm, an eye-tracking task that measures attention to food cues, and an EAH paradigm. Additionally, children will complete a questionnaire-based media multi-tasking scale.

Children will be randomized to complete the multi-task, sustained attention, or control condition of the media multi-tasking paradigm during their first visit and will complete the alternate conditions during their second and third visits. The experimental flow for individual laboratory visits is shown in **Figure 2**.

[figure not shown]

**Participant recruitment and enrollment.** We will recruit 150 children, aged 13-17-years-old using listservs, community postings and in-person recruitment in family-centered organizations such as schools, pediatric clinics, and community centers, and postings on social media platforms such as Facebook. Participants may be recruited under study-specific recruitment efforts and/or our general recruitment efforts for all the studies our lab is currently running. In addition, we will also recontact participants from a list of participants who have previously enrolled in studies in our lab. Parents of these children have consented to being contacted for future studies. We will periodically send all families in our database e-cards to thank them for their participation in our studies and also to let them know that we are recruiting participants for multiple studies. The study will be promoted as a study to investigate how children process information from different types of media; specific study goals will be concealed from children until the end of the study to prevent biasing participant behavior. However, parents of children will be told the true nature of the study prior to providing consent for their child's participation so that they can make an informed decision. We will ask the parent not to share the true purpose of the experiment until the study is over. Exclusion criteria will include inadequate English proficiency, a vision disorder that is not corrected with corrective lenses, and relevant food allergies. Exclusion criteria will be confirmed by the parent during the initial consent procedure via telephone. After initial parental consent is obtained verbally via telephone, study staff will schedule three dinnertime or lunchtime appointments and ask that children eat normal meals and snacks the day of the appointment, but refrain from eating within 45 minutes of their appointment. At the appointment, staff will obtain informed consent/assent. Following consent, children will complete the experimental flow in Figure 2.

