## APPROACH

### Main Study

We will achieve our aims by having 13-17-year-olds visit the laboratory on three occasions to complete each of three tasks: a media multi-tasking paradigm, an eye-tracking task that measures attention to food cues, and an EAH paradigm. Additionally, children will complete a questionnaire-based media multi-tasking scale. Children will be randomized to complete the multi-task, sustained attention, or control condition of the media multi-tasking paradigm during their first visit and will complete the alternate conditions during their second and third visits. The experimental flow for individual laboratory visits is shown in Figure 2.

**Preload meal.** In order to control for satiety, children will be fed a standardized palatable dinner at the beginning of the study using established methods (48).

**Multi-tasking experimental manipulation.** Immediately following dinner, children will complete one of three conditions (attentional training, acute media multitask, or control) in a modified version of the Go/No-go task to simulate media-multitasking.

**Attentional training.** A Go/No-go task was used to train sustained attention. For the task, a blue or yellow dot briefly appeared for between 20 - 1500 msec and then disappeared. Participants were instructed to respond to the blue dot by pressing the space bar as quickly as possible (Go trials) and were told not to respond when presented with a yellow dot (No-go trials). At random intervals between 2000 – 5000 msec the messaging bot would ding and send participants a text message. The text message included questions about random facts; for example, how many teeth does an alligator have? Participants were instructed to ignore the messages and focus on the Go/No-go task. By asking participants to practice ignoring incoming messages and focus on a task designed to increase sustained attention, the training condition was designed to reduce acute media multitasking and increase sustained attention. Participants completed 100 Go trials and 100 No-go trials randomized on a trial-to-trial basis. There was a total of 60 messages sent to participants.

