**Attention to peripheral cues.** Immediately following the multi-tasking experimental manipulation, children will play a game of Tetris that measures attention to peripheral cues using eye-tracking. On either side of the game screen are pictures of food and animals that change periodically. Study staff will set up children with the task, provide directions, have children do a practice trial game, and clarify directions if necessary. The food cue is chosen at random on a game-to-game basis. To encourage gameplay concentration, children are encouraged to complete as many games as possible within 10 minutes. This game has high ecological validity because it mimics Internet advergames that are used to advertise products to children (2). We will use established eye-tracking metrics to measure attention to food cues. The amount of attention given to peripheral cues while playing the video game Tetris will be calculated for each participant after they completed each experimental condition. Areas of interest will be created around distractor images, defined as the area of the image, 250 X 250 pixels. First fixation duration will be measured as the average amount of time an adolescent spent fixating a distractor the first time that they looked at it. Cumulative fixation duration will be calculated as the total amount of time participants spent fixating distractors, summed over all fixations. For both measures, a fixation duration will be defined as any stationary period lasting at least 100 milliseconds. Eye-tracking will be recorded using the EyeLink 1000 Plus (SR Research, Ottawa, Ontario, Canada). The EyeLink is a robust desktop configuration that also includes facial recognition software to monitor head movements. This ability to compensate for head movements is particularly useful because it assures that when participants look away from the stimulus and then return to it, the system will automatically reacquire the eye. Critically, the video used to track the eyes is not saved and the person's likeness is never recorded.

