**Potential covariates.** We will assess potential covariates for potential inclusion in analyses for Aims 1-3. Given the association between exercise and increased attentional processing in preadolescent children (61), we will assess usual **physical activity** using the ActiGraph GT3X-BT triaxial accelerometer (ActiGraph LLC, Pensacola, FL) for 7 days between the first and second visit using established methods (62-64). Relatedly, it is important to record physical activity to isolate the effect of media multi-tasking on cued eating, from the effect of general sedentary behavior that media multi-tasking is potentially a proxy. Children will also be asked to self-assess their **pubertal maturation** using the Pubertal Development Scale, which has shown strong validity and acceptability in our age group (65-67). Before administering this scale, the experimenter will emphasize that responses are voluntary, and that if the child simply does not understand some questions, his/her parent will offer responses. We will have children report on their **media exposure** using a questionnaire adapted from the Kaiser Foundation (14), and their **health knowledge and attitudes about the provided food** (68). Parents will report on their child's **sleep duration** using the Adolescent Sleepiness Scale, the Adolescent Sleep-Wake Scale, and the Adolescent Sleep Hygiene Scale (69), eating behaviors using the child eating behavior

questionnaire (CEBQ) (71), and **sociodemographic variables** (i.e., education, household income, race, and ethnicity). **Height and weight** will be measured using standard methods (72) to calculate age- and sex-specific **BMI z-scores** (73). These variables will be collected via a parent questionnaire that will be completed by the parents via an online questionnaire sent securely through RedCap.

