#### 4. Analysis

**Describe any qualitative tests and measures as well as quantitative methods:**

Our primary outcomes of interest will be  $\Delta$  first fixation duration to peripheral cues,  $\Delta$  cumulative fixation to peripheral cues, and  $\Delta$ EAH and our primary exposures will be the multi-task vs. control condition and the sustained attention task vs. control. We will first assess main effects of the acute tasks by using multivariable linear regression to fit  $\Delta$  attention eye-tracking metrics on  $\Delta$ EAH. Cohen's power calculation for regression, and setting alpha to  $P < .05$ , two-tailed, we calculated 80% power to detect a moderate effect size ( $f^2 = .15$ ) for main effects. To test for moderation, we will then repeat the main effects models stratifying the sample by the median of usual media multi-tasking. We will conduct a formal test for interaction by repeating the main effects models on the entire sample with the acute task, usual media multi-tasking, and the product of the acute task and usual media multi-tasking as the independent variables of interest. A Wald test on the product term  $P < 0.10$  will be considered evidence of a statistically significant interaction.

To examine the effects related specifically to food images, we will repeat all analyses using first fixation bias and cumulative fixation bias to food cues as our outcomes of interest. A first fixation bias to food cues was calculated by computing the difference between first fixation duration to food and animal images. A positive value represents that a child looked longer the first time they fixated a food versus toy distractor. A cumulative gaze duration bias to food cues was calculated by computing difference between cumulative fixation duration to food versus toy animal distractors. A positive number indicates that a child spent more total time looking at food versus toy distractors.

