We assessed power to detect a significant correlation between each predictor and our outcome using Cohen's method for Pearson's correlation coefficient (74). Using 107 participants (assuming a retention rate of 85%), 80% power, and a Type I error rate of 0.05 (two-tailed), we calculated that Aim 1 is powered to detect a moderate effect size of  $|r \geq 0.27|$  for either predictor with EAH. Cross referencing this effect size and our power analysis parameters with the empirical power tables for mediation created by Fritz and Mackinnon (75), we found that that our study is 80% powered to detect if media multi-tasking fully mediates the relationship between attention to food cues and EAH.

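### No visit term is named and the order of visits 2 and 3 is not stated; where change in attention is related to change in EAH, drift common to all children in both measures can create a false association

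*Combined protocol and SAP*

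**What the plan says.** The combined protocol and SAP describes a three-visit, within-child comparison of three conditions.

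- **Order.** Section 3 and the Main Study part of the Approach randomise the condition at visit 1: "Children will be randomized to complete the multi-task, sustained attention, or control condition of the media multi-tasking paradigm during their first visit". Of the rest they say only that children "will complete the alternate conditions during their second and third visits". No sequence list or counterbalancing is described. Figure 2 is not reproduced, but the text presents it as the flow within a single visit.
- **Measurement.** Attention to peripheral cues "will be calculated for each participant after they completed each experimental condition", so there is one value per condition and therefore one per visit.
- **Covariates.** "We will assess potential covariates for potential inclusion in analyses for Aims 1-3". The list covers activity, puberty, media exposure, food knowledge and attitudes, sleep, eating behaviour, sociodemographics and BMI z-score. Visit number and sequence are not on it.
- **Model.** Section 4 states that "our primary exposures will be the multi-task vs. control condition and the sustained attention task vs. control". It then says "We will first assess main effects of the acute tasks by using multivariable linear regression to fit", and the sentence goes on to name the change in the eye-tracking metrics on the change in EAH. The change score is not defined. No visit or period term appears in the main-effects, stratified or interaction models.
- **Power.** The last paragraph of Section 4 gives a detectable correlation of 0.27 for either predictor with EAH at 107 participants. It also claims power to detect whether "media multi-tasking fully mediates the relationship between attention to food cues and EAH". It does not say that these analyses use change scores.

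**The concern.** If children take the conditions in different orders, the gap in visit number between the task and control sessions differs between children. A child who does control first and the task third has a gap of +2; a child who does them the other way round has a gap of -2. If attention to the distractors and snack intake both change with repeated visits (familiarity with the game, the room, the snacks), the same gap enters both change scores and correlates them, with no true link between attention and eating.

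Balancing the orders does not prevent this. Balance protects the average task-control difference, not the association between two differences. The link from attention to eating is the mechanism proposed in Section 2, so a significant result could partly reflect repeated testing.

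The unstated order is a separate exposure. If the orders are not balanced, drift also shifts the average task-control contrasts.

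**Working it through.** **Inputs from the documents:** 107 analysed, two-sided 5% test, three visits, one measurement per condition (Section 4; Main Study). **Assumed:** drift per visit, *d*, in within-child SD units; independent visit errors with SD 1; no true association between the two change scores. Drift is not given, so a range is shown.

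**1. The plan's own figure.** Detectable r = tanh[(1.960 + 0.842)/√(107 − 3)] = tanh(0.2747) = 0.268. The stated 0.27 is reproduced.

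**2. False correlation with six balanced orders.** The visit gap between task and control is ±1 in four orders and ±2 in two. Its mean is 0 and its variance is (4×1 + 2×4)/6 = 2. The error variance of a change score is also 2. With drift d_a in attention and d_e in EAH, the covariance is 2·d_a·d_e, so

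r = d_a·d_e / √[(1 + d_a²)(1 + d_e²)].

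For a step of size s after visit 1 in both measures, the gap in the step indicator has variance 2/3, so r = s²/(3 + s²).

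**3. Type I error of the test relating the two change scores.** The normal approximation uses atanh(r)·√104 as the shift. It is set beside simulation (40,000 trials per scenario):

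| Drift in both measures | r | Approximation | Simulated, no visit terms | Simulated, with visit-difference terms |
|---|---|---|---|---|
| 0.1 per visit | 0.01 | 5.1% | 5.3% | 5.1% |
| 0.2 per visit | 0.04 | 6.8% | 6.7% | 5.0% |
| 0.25 per visit | 0.06 | 9.2% | 9.1% | 5.0% |
| 0.42 per visit | 0.15 | 33.8% | 34.5% | 5.1% |
| Step of 0.5 after visit 1 | 0.08 | 12.3% | 12.5% | 5.2% |
| 0.42 in one measure only | 0 | 5% | 5.1% | 5.2% |

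Unequal drift matters less: 6.8% for 0.42 with 0.1, and 5.5% for 0.25 with 0.1. Smaller independent repeats of the simulation agree within about one percentage point. Section 9 gives 120 as the sample size; 120 × 0.85 = 102, and at 102 the rates are 8.9% (0.25), 32.6% (0.42) and 12.2% (step of 0.5).

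On scale: 0.42 within-child SD equals 0.3 total SD if the within-child correlation is 0.5 (0.3/√0.5 = 0.42). It amounts to 0.84 within-child SD from visit 1 to visit 3, which is a large drift.

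**4. Task-control contrast if the orders are not balanced.** Suppose, for illustration, that the two remaining conditions always run in list order (multi-task, attention, control). The three orders put multi-task at visits 1, 2, 2 (mean 1.67) and control at visits 3, 3, 1 (mean 2.33). The contrast is biased by −0.67 of the per-visit drift. At d = 0.2 the bias is −0.133. The variance of the change is 2 + 0.04 × (2 − 0.444) = 2.062. The shift is 0.133 × √107/√2.062 = 0.96, which gives a false-positive rate of about 16%. With six balanced orders or a cyclic Latin square, all mean positions are 2 and the bias is zero.

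**5. What visit terms do not remove.** With zero average drift but a child-specific slope shared by both measures, type I error without and with visit terms is 9.0% and 8.8% at a slope SD of 0.25, and 34% and 33% at 0.42.

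**The case against.** The strongest case against is that the stated primary exposures are the conditions against control. If those alone are the exposures and the orders are balanced, drift adds noise but no bias. That is correct. The difficulty with two change scores then arises only where attention is related to EAH. Against this, the literal wording of the main-effects step does relate them.

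The size is also assumed. At 0.1 per visit the effect is negligible, both measures must drift, and the 34% needs a large drift. Concealed aims, a practice game and a standardised preload meal all work against drift. This stands, and is why the result is given as a range. It is also fair that a multivariable regression does not exclude a visit term; the point is that none is named.

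Four stronger inferences are tempting but unsupported:

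- **That the randomised contrasts are biased.** The documents do not state the orders, so neither balance nor imbalance can be inferred.
- **That the correlation and mediation analyses are affected.** That paragraph does not mention change scores, and its mediator, media multi-tasking, may be the between-child questionnaire score. The issue applies only if those analyses are run on changes.
- **That visit terms would clear the attention-EAH link of all drift.** Step 5 shows that they do not.
- **That main-effects power is safe.** A one-coefficient test of f² = 0.15 with 107 children has 97.8% power, but Section 4 states 80%. At 107 that matches a joint test of about seven or eight coefficients (81.9% and 79.4%). The plan does not say which test is meant, so no reassurance follows.

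**Conclusion.** The concern holds in a limited form. The plan names no visit term and does not state the order of visits 2 and 3, although each change score, read as task minus control, compares two visits. Where change in attention is related to change in EAH, common drift in both measures inflates the false-positive rate even with balanced orders. The inflation is minor below about 0.25 within-child SD per visit (9% at that value) and serious only with large drift (34% at 0.42) or a clear step after the first visit (about 13% at 0.5 SD). If only one measure drifts there is no inflation.

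The task-control contrasts are sound if the orders are balanced. The plan does not show that they are, and the 16% figure is one illustration of what imbalance could do. All of these sizes rest on assumed drift and independent visit errors. Nothing in the documents shows that drift occurs. The case for acting is that visit number is known for every session and the adjustment is cheap.

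**What to change.** 1. Define the change score and state whether the exposure in the main-effects step is condition or change in attention.
2. Include categorical visit number in every condition and interaction model, for example condition plus visit with a random child intercept.
3. In any model relating change in attention to change in EAH, add the categorical visit-difference terms (2 df). Apply the same to the correlation or mediation analyses if they are run on changes. A linear position difference alone is not enough: for a 1.0 SD step after visit 1 it leaves type I error at 12.4%, against 4.9% with the categorical terms.
4. State the condition orders used. For any children not yet randomised, balance all six orders.
5. State with the conclusion that the adjustment removes drift common to all children, not child-specific drift shared by both measures.

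**Cost:** two degrees of freedom and a few sentences; no new data, visits or participants. At 107 the detectable correlation moves from 0.268 to tanh(2.802/√102) = 0.270. The tasks are described in the past tense, so allocation may already be complete; the balancing in item 4 would then not apply, but the rest would.
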